Study design:	
As a first step to developing new glucagon infusion delivery strategies for hypoglycemia, development of computer algorithms to predict timing and severity of hypoglycemia onset has been initiated, in collaboration with computational scientists at Harvard University School of Engineering. We have analyzed data collected from clinically-indicated diagnostic continuous glucose monitoring systems (iPRO CGMS) obtained from patients enrolled in the hypoglycemia clinic at the Joslin Diabetes Center. Extracted data, including continuous glucose monitoring sensor glucose values, age, gender, and body mass index, and food and activity logs, were used to develop computational algorithms to allow prediction of hypoglycemia.
 
This will be a Phase 2a, single-center, open-label, proof-of-concept study designed to test the ability of the control algorithm to detect and direct timing of G-Pump™ glucagon infused from an OmniPod® pump to prevent hypoglycemia in patients with post-bariatric hypoglycemia syndrome. While the algorithm will provide an alert as to when glucagon

	should be dosed to prevent hypoglycemia, there will be no automation in this clinical trial and it will ultimately be up to the physician to initiate dosing via the OmniPod® controller.
Study location:	Joslin Diabetes Center, Boston, MA USA.
Study duration:	The total length of the study will be approximately one week per patient, and involve up to two infusions of G-Pump™ glucagon at a single visit. The total time for enrollment and treatment will be approximately 3 months.
Sample size:	For this proof-of-concept study, success will be defined as meeting the primary endpoint in 3 of 5 participants. If this is not achieved, the algorithm will be revised, and an additional 5 participants may be recruited for additional study.
Subjects:	Adult male or female patients with post-bariatric hypoglycemia syndrome
Inclusion Criteria:	
1. Males or females diagnosed with ongoing post-bariatric hypoglycemia with prior episodes of neuroglycopenia, unresponsive to dietary intervention (low glycemic index, controlled carbohydrate portions) and trial of acarbose therapy at the maximally tolerated dose.2. Age 18-65 years of age, inclusive, at screening.3. Willingness to provide informed consent and follow all study procedures, including attending all scheduled visits.
Exclusion Criteria:	
1. Documented hypoglycemia occurring in the fasting state (> 12 hours fast);2. Chronic kidney disease stage 4 or 5;3. Hepatic disease, including serum ALT or AST greater than or equal to 3 times the upper limit of normal; hepatic synthetic insufficiency as defined as serum albumin < 3.0 g/dL; or serum bilirubin > 2.0;4. Congestive heart failure, NYHA class II, III or IV;5. History of myocardial infarction, unstable angina or revascularization within the past 6 months;6. History of a cerebrovascular accident;7. Seizure disorder (other than with suspect or documented hypoglycemia);8. Active treatment with any diabetes medications except for acarbose;9. Active malignancy, except basal cell or squamous cell skin cancers;10. Personal or family history of pheochromocytoma or disorder with increased risk of pheochromocytoma (MEN 2, neurofibromatosis, or Von

	
Hippel-Lindau disease);
 
11. Known insulinoma;
 
12. Major surgical operation within 30 days prior to screening;
 
13. Hematocrit $\leq 33\%$;
 
14. Bleeding disorder, treatment with warfarin, or platelet count $< 50,000$;
 
15. Blood donation (1 pint of whole blood) within the past 2 months;
 
16. Active alcohol abuse or substance abuse;
 
17. Current administration of oral or parenteral corticosteroids;
 
18. Pregnancy and/ or Lactation: For women of childbearing potential: there is a requirement for a negative urine pregnancy test and for agreement to use contraception during the study and for at least 1 month after participating in the study. Acceptable contraception includes birth control pill / patch / vaginal ring, Depo-Provera, Norplant, an IUD, the double barrier method (the woman uses a diaphragm and spermicide and the man uses a condom), or abstinence.
 
19. Use of an investigational drug within 30 days prior to screening.
 
20. There will be no involvement of special vulnerable populations such as pregnant women, prisoners, institutionalized or incarcerated individuals, or others who may be considered vulnerable populations.

--	---

Brief outline of treatments:	
Methods:
 
Visit Day 1 - Screening:
 
• Adult male or female patients with PBH will be recruited from the hypoglycemia clinic at Joslin.• Patients will undergo a history and physical examination, with particular emphasis on inclusion and exclusion criteria.• Blood and urine samples will be obtained for screening laboratory testing including hemoglobin A1c, CBC, comprehensive chemistry, urinalysis, and pregnancy test (if applicable).• Consent forms will be reviewed in detail with potential participants. 
Visit Day 2 - CGM Sensor Placement:
 
• Two continuous glucose monitor sensors (Dexcom® G4 Platinum) will be placed on the anterior abdominal wall (to ensure sensor availability and calibration for visit day 3). Participants will be provided a glucometer and instructed in both sensor insertion and calibration techniques.• If patient has prior experience with sensor insertion and calibration
------------------------------	--

then this visit may occur concurrent with visit 1.

Visit Day 3 – Mixed Meal Testing (</= 3 days following Visit 2):

- Subjects will arrive in the morning after an overnight fast.
- An intravenous line will be inserted for blood sampling and to provide intravenous access. Placement of the Dexcom sensor will be verified, and calibration verified using at least 2 venous blood glucose samples obtained 15 minutes apart.
- An OmniPod® containing G-Pump™ glucagon will be inserted.
- Two blood samples will be obtained for measurement of plasma glucose (via YSI analytical device) immediately and for subsequent hormonal assays.
- The subject will then be asked to drink a liquid mixed meal containing 60 g of carbohydrates, e.g. Boost® Nutritional Drink, over 10 minutes.
- Blood samples will be collected for immediate (in room) glucose measurements (YSI) every 10 minutes, and hormonal profiles at 10, 20, 30, 60, 90, 120, 150, and 180 minutes. Once venous glucose levels fall below 90 mg/dl, glucose will be measured at 5 minute intervals (YSI). This blood sampling series will conclude once sensor glucose levels fall to <75 mg/dl. (See below for subsequent sample timing after clock is reset when glucagon is delivered.)
- The open-loop system will be set to recognize sensor glucose values <75 mg/dl, triggering an alert to the physician, who will deliver a bolus of 150 or 300 µg of glucagon via the pump, with the goal of preventing further decline in glucose values. Time will be reset to 0 at the time of glucagon delivery.
- Plasma glucose will be measured (YSI) at 5, 10, 20, 30, 45, 60, 90, and 120 minutes after glucagon administration to ensure successful treatment and glucose stability, and glucagon levels will be analyzed concurrently to determine magnitude of increase above baseline.
- If the open-loop algorithm issues a predictive alert or detects a sensor glucose level under 75 mg/dl within 30-120 minutes after the first dose of glucagon, a second dose of glucagon (either 150 micrograms if a predicted hypoglycemia alert, or 300 micrograms if sensor glucose is under 75 mg/dl) will be administered. If a second dose of glucagon is given, glucose levels will be monitored every 15 minutes for an additional 60 minutes.
- At time of alarm trigger and before each administration of glucagon, the Edinburgh Hypoglycemia Symptoms Score will be

assessed. This will be repeated at 15, 30 and 60 minutes following glucagon infusion.

- Thirty minutes after the last glucagon treatment, the OmniPod® pump will be removed, and lunch will be provided.
- Venous blood glucose will be monitored every 15 minutes for at least 2 hours to ensure stability prior to discharge from the clinical research unit. Prior to discharge, the pump insertion site will be examined, and sensors will be removed. Patient will be given a snack on discharge.
- Sensors will be downloaded for subsequent analysis of appropriateness of alert timing and trigger for glucagon bolus delivery.
- Blood samples collected during this visit will be processed and stored at -80 until analysis for insulin and incretin hormone levels (to verify typical patterns in response to meal ingestion), for baseline levels of cortisol, and for glucagon, to assess endogenous responses as well as post-bolus plasma levels.

Follow-Up Phone Call (1 to 3 days following Visit 3)

Biostatistical Considerations:	
All subjects who have received at least one dose of glucagon will be included in the data analysis set. Adverse events, vital signs, physical examination, laboratory safety variables (Screening to Final Visit), EKG (Screening to Final Visit), and local tolerability data will be reviewed and summarized on an ongoing basis during the study to evaluate the safety of subjects. Safety data will be presented in tabular and/or graphical format and summarized descriptively, where appropriate.
 
Sensor and glucagon delivery request will be collected and evaluated for specificity and response time.
 
Glucagon, insulin, and incretin plasma concentration profiles will be analyzed with commercially available analytical methods and examined using repeated-measures ANOVA.
 
Success will be defined as meeting the primary endpoint in 3 of 5 participants. If this is not achieved, the algorithm will be revised, and an additional 5 participants may be recruited for additional study.

--------------------------------	---

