**NCT02733588**

**Document Date: February 13, 2017**

## Statistical Analysis Plan for Protocol XSGO-PB01

**Analysis Population.** Participants with a history of RYGB surgery and PBH with neuroglycopenia, uncontrolled on medical nutrition therapy and medications, were recruited from the hypoglycemia clinic. Exclusion criteria included fasting hypoglycemia, known insulinoma, major systemic illness, pregnancy, substance or alcohol abuse, recent steroid or investigational drug exposure, and use of medications (beyond hypoglycemia treatment) known to affect insulin secretion or action. The Joslin Diabetes Center Committee on Human Studies approved the study. Written informed consent was obtained from all participants. Six females and one male were enrolled. Two participants enrolled twice, in different stages of system development. All enrolled participants were included in the analysis.

**Study endpoints.** This iterative development clinical study was designed to evaluate the primary endpoints of safety and feasibility of the proposed system to predict and prevent severe hypoglycemia in patients with PBH. Secondary outcomes included prediction of imminent hypoglycemia by the automatic monitoring algorithm, minimization of time below a prespecified threshold (<75 mg/dL) using glucagon delivery, prevention of severe postprandial hypoglycemia (plasma glucose <60 mg/dL), and prevention of rebound hyperglycemia (plasma glucose >180 mg/dL) after glucagon delivery.

**Statistics.** As an algorithm iterative development study, sample size was not determined by a power calculation. Statistical analyses were performed using GraphPad Prism (GraphPad Software, La Jolla, CA). Normally distributed data were expressed as mean  $\pm$  standard deviation and skewed data were expressed as median with interquartile range. Normality was determined using the Shapiro-Wilk test. Statistical significance was determined with the Wilcoxon signed-rank test.

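### Doses follow the sensor or algorithm, outcomes are scored on plasma, and other treatment and lunch have no scoring rule, so prevention and rebound results may not be attributable to the system

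*Protocol*

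**What the plan says.** **Triggers (Protocol, Visit Day 3).** For the first dose: "The open-loop system will be set to recognize sensor glucose values <75 mg/dl, triggering an alert to the physician". For the second: "If the open-loop algorithm issues a predictive alert or detects a sensor glucose level under 75 mg/dl within 30-120 minutes after the first dose". Study design adds that nothing is automated: "it will ultimately be up to the physician to initiate dosing via the OmniPod® controller".

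**Plasma readings (Protocol, Visit Day 3).** YSI glucose is read in the room every 10 minutes after the meal. Then: "Once venous glucose levels fall below 90 mg/dl, glucose will be measured at 5 minute intervals (YSI". The series has a sensor-based end: "This blood sampling series will conclude once sensor glucose levels fall to <75 mg/dl". After a dose, plasma is read at 5, 10, 20, 30, 45, 60, 90 and 120 minutes.

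**Symptoms (Protocol, Visit Day 3).** The schedule begins "At time of alarm trigger and before each administration of glucagon, the Edinburgh Hypoglycemia Symptoms Score" and repeats the score 15, 30 and 60 minutes after glucagon.

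**Lunch (Protocol, Visit Day 3).** The pump comes off and lunch is served 30 minutes after the last glucagon treatment.

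**Outcomes.** The protocol's Objectives use <60 and >180 mg/dl without saying whether sensor or plasma is meant. The SAP, Study endpoints, names plasma: "prevention of severe postprandial hypoglycemia (plasma glucose <60 mg/dL", with rebound as plasma >180 mg/dL after glucagon.

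**Analysis set.** Biostatistical Considerations takes participants with at least one glucagon dose. The SAP, Analysis Population, takes everyone enrolled.

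**The concern.** The system acts on one measurement and is judged on another. A low in-room plasma value changes how often blood is drawn, and nothing else in the written plan depends on it. If the sensor reads high and no alert sounds, the plan states no response. Unless the physician gives glucagon anyway, it schedules no symptom score either.

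Two results are exposed. A participant kept above 60 mg/dl by something other than study glucagon could be credited to the system, or could disappear from the denominator. A plasma value above 180 mg/dl after lunch could be reported as rebound from glucagon. In addition, the symptom record has its gap in sessions where detection failed, which are the most informative ones for the safety of an alert system.

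**Working it through.** The plan gives no figure to reproduce; the SAP says the sample size did not come from a power calculation. The check sets the rules side by side and adds simple arithmetic.

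**1. How far apart sensor and plasma must be.**
- No threshold alert means sensor ≥75 mg/dl. Plasma <60 without that alert therefore needs a sensor more than 75 − 60 = 15 mg/dl above plasma (15/60 = 25%).
- At plasma 62, a sensor 75 − 62 = 13 mg/dl too high is enough. The predictive algorithm would also have to be silent.

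**2. Would a true plasma value <60 be seen?** Assume a fall of 1 to 3 mg/dl per minute (not in the documents). From 75 to 60 takes 15/1 = 15 to 15/3 = 5 minutes, or three to one of the 5-minute intervals. An alert-free fall below 60 would usually be recorded, and counts as a failure under the SAP. Misclassification therefore needs other treatment given while plasma is still 60 or above.

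**3. Effect of one such participant.** Suppose 3 of 5 were protected by the system, and one of the other two was undosed and treated by other means at plasma 60 or above.

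| Scoring | Rate |
|---|---|
| Counted as not prevented | 3/5 = 60% |
| SAP, all enrolled, plasma never <60 | 4/5 = 80% |
| Protocol, dosed only | 3/4 = 75% |

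Both written sets give a better figure than 60%. With the SAP's 7 people, two of them enrolled twice, there are 7 + 2 = 9 enrolments, and one reclassification moves the rate by 1/9 = 11 points. A participant who had already been dosed would stay in both sets.

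**4. How likely is at least one missed alert?** The documents give no miss rate. For an assumed rate m per participant, the chance is 1 − (1 − m)^5.

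| m | At least one in 5 |
|---|---|
| 5% | 23% |
| 10% | 41% |
| 20% | 67% |
| 30% | 83% |

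This is the chance of a missed alert, not of a misclassified participant, which also requires other treatment before plasma reaches 60. The 3-of-5 success rule itself tolerates two participants who do not meet the algorithm endpoint.

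**5. Symptom scores.** A session with an alarm and one dose has a score at the alarm or before the dose, plus 15, 30 and 60 minutes: at least 4. A session with neither alarm nor dose has 0.

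**6. Lunch.** With one dose and lunch at 30 minutes, the samples at 45, 60, 90 and 120 minutes, 4 of 8, come after food. The protocol also opens the second-dose window at 30 to 120 minutes after the first dose, while pump removal and lunch come 30 minutes after the last treatment. These timings must be reconciled before lunch can serve as a clear end of the window. For a participant who is never dosed, lunch has no stated time.

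**The case against.** The strongest reply is that the physician starts every dose, sees the YSI values in the room and could give glucagon without an alert, which would itself call for a symptom score. Two sensors are placed, calibration is verified against venous samples, intravenous access is in place, and adverse events are collected. The protocol is in synopsis form, so silence about other treatment is weak evidence that no rule exists. Treatment other than glucagon is an assumption, and the Edinburgh score is not a named endpoint.

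Most of this stands, and it rules out several stronger readings that a reader might infer:
- That a participant with plasma 58 and sensor 80 would be counted as prevented. Plasma 58 is a recorded failure under the SAP.
- That symptoms also go unscored after dosing. The 15, 30 and 60-minute scores follow each dose whatever the alarm does.
- That severe hypoglycemia is defined on plasma throughout. Only the SAP says so.
- That other treatment would necessarily count as prevention. It could, under the all-enrolled set; the dosed-only set drops an undosed participant.

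What the reply does not remove is the scoring gap. The physician's discretion is not tied in writing to a low plasma value. Both analysis sets err in the system's favour when an undosed participant is treated early. Lunch is no assumption: it is scheduled for every dosed participant.

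**Conclusion.** The point holds in this limited form and should be corrected. Followed literally, the plan can credit the system with the effect of other treatment given at plasma 60 mg/dl or above, cannot attribute a post-lunch value above 180 mg/dl to glucagon, and schedules no symptom score when there is neither alarm nor dose. One affected undosed participant lifts a prevention rate of 60% to 80% or 75%. That figure assumes that such treatment occurs and that a cohort of 5 is reported; the miss rates above are illustrative. The lunch problem needs no such assumption.

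A reader might go on to infer that the study's go/no-go decision is compromised. The documents do not support that: the 3-of-5 rule is on the algorithm's detection and timing, not on prevention.

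**What to change.** 1. **Protocol.** Reconcile the in-room plasma readings with the sensor and algorithm triggers, so that the text says how a low plasma value without an alert is handled. Reconcile pump removal and lunch with the second-dose window. The clinical rules are for the sponsor to state.
2. **SAP.** Use one analysis set that keeps undosed participants. End the outcome window at scheduled lunch, and state an end for undosed sessions, where lunch has no stated time. Within the window, count any unscheduled glucose-raising treatment other than study glucagon as severe hypoglycemia not prevented. Leave plasma values after such treatment, or after lunch, out of the rebound and time-based outcomes. Record the time of any such treatment.
3. **Symptoms.** Also take the Edinburgh score at the first plasma value <60 mg/dl and just before any non-study glucose-raising treatment, whether or not an alarm has sounded. A pre-meal score is optional.

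The cost is some wording, one time-stamped field and one or two short questionnaires. The rebound outcome loses plasma values (4 of 8 per single-dose session on the literal schedule), and the prevention figure may be less favourable.

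### From 10 minutes after glucagon the listed plasma samples are 10 to 30 minutes apart, so brief values below 60 mg/dl can go unseen and be counted as prevented

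*Protocol*

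**What the plan says.** All sampling rules are in the protocol synopsis, Brief outline of treatments, Visit Day 3.

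- **Before glucagon.** "Blood samples will be collected for immediate (in room) glucose measurements (YSI) every 10 minutes". Then: "Once venous glucose levels fall below 90 mg/dl, glucose will be measured at 5 minute intervals (YSI"). The series has an end point: "This blood sampling series will conclude once sensor glucose levels fall to <75 mg/dl". The clock restarts at zero when glucagon is delivered.
- **After glucagon.** "Plasma glucose will be measured (YSI) at 5, 10, 20, 30, 45, 60, 90, and 120 minutes after glucagon administration".
- **After a second dose**, possible 30 to 120 minutes after the first: "glucose levels will be monitored every 15 minutes for an additional 60 minutes".
- **Before discharge.** "Thirty minutes after the last glucagon treatment, the OmniPod® pump will be removed, and lunch will be provided". The next item reads: "Venous blood glucose will be monitored every 15 minutes for at least 2 hours to ensure stability prior to discharge".

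The SAP, under Study endpoints, lists among its secondary outcomes "prevention of severe postprandial hypoglycemia (plasma glucose <60 mg/dL"). It also lists keeping time below 75 mg/dL to a minimum, without saying whether plasma or sensor values are used or how minutes are derived. The protocol's Objectives likewise name no glucose source for values below 60 or for minutes in the 60-180 range. Two sensors are worn until shortly before discharge, but the protocol assigns their download only to judging alert timing and the bolus trigger.

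**The concern.** The plan treats 5-minute sampling as appropriate when glucose is below 90 and falling, and ends that series at the alert. The outcome period starts with the dose. From 10 minutes after it, the listed samples move progressively further apart, including in the 30-120 minute window where the protocol itself allows for a further fall.

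If prevention means that no plasma sample was below 60, sampling gaps can hide a low but, assay error aside, cannot create one. Any error in that count therefore favours the system. The numbers are small: the SAP reports seven people, two of whom enrolled twice. That is seven or nine sessions, depending on how the enrolments are counted and assuming one session each. One misclassified session moves the prevention rate by 1/9 = 11 to 1/7 = 14 percentage points.

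**Working it through.** The plan gives no figure to reproduce, so the check asks what share of low episodes could fall entirely between samples.

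**Inputs from the documents**
- Listed post-dose times 5, 10, 20, 30, 45, 60, 90 and 120 minutes give gaps of 5, 5, 10, 10, 15, 15, 30 and 30.
- If the pre-discharge checks run every 15 minutes from 30 minutes, the gaps are 5, 5, 10, 10 and then six of 15.
- The second-dose schedule read alone gives four gaps of 15 over 60 minutes.

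**Assumptions (not in the documents).** An episode below 60 lasts D minutes, with D from 5 to 30, and its onset is uniform over the window.

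**Formula.** For a window of W minutes with gaps Gᵢ, the share unseen is Σ max(0, Gᵢ − D) / (W − D). Example for D = 5 on the listed times: (0+0+5+5+10+10+25+25)/(120−5) = 80/115 = 70%.

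| D (min) | Listed times, 0-120 | With 15-min checks from 30, 0-120 | Second-dose schedule, 0-60 |
|---|---|---|---|
| 5 | 80/115 = 70% | 70/115 = 61% | 40/55 = 73% |
| 10 | 50/110 = 45% | 30/110 = 27% | 20/50 = 40% |
| 15 | 30/105 = 29% | 0% | 0% |
| 20 | 20/100 = 20% | 0% | 0% |
| 25 | 10/95 = 11% | 0% | 0% |
| 30 | 0% | 0% | 0% |

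With a sample every 5 minutes throughout, the share is 0% for any D of 5 or more.

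**Where the gaps bite (listed times only)**
- 0-30 minutes: D = 5 gives 10/25 = 40%; D = 10 or more gives 0%.
- 60-120 minutes: D = 10 gives 40/50 = 80%; D = 15 gives 30/45 = 67%; D = 20 gives 20/40 = 50%.

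**Time below 75, if taken from plasma by linear interpolation.** Assume a V-shaped dip reaching 65 from a level of 90. The error can go either way:
- A 30-minute dip lying exactly between the 60- and 90-minute samples is estimated at 0 minutes, an error of −30.
- A 10-minute dip centred on the 90-minute sample reads 65 there and 90 at 60 and 120 minutes. The interpolated line crosses 75 after 30 × 10/25 = 12 minutes on each side, so the estimate is 24 minutes, an error of +14.
- Averaged over positions of the dip, the mean error is −5.4, −6.2, −6.6 and −4.2 minutes for dips of 10, 15, 20 and 30 minutes.

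**The case against.** A reader might infer that sampling thins as soon as glucagon is given, that lows are in fact missed, and that prevention is in fact overstated. The documents do not support that.

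- Samples at 5 and 10 minutes keep the 5-minute rate going for 10 minutes. No episode of 10 minutes or more can be missed in the first 30. The pre-dose 5-minute rate itself applies only below 90; above that it is 10 minutes.
- The 15-minute venous checks may cap every gap at 15 minutes, in which case any episode of 15 minutes or more is seen. Whether they do is unclear. They follow a step timed from the last glucagon treatment, and a second dose can come as late as 120 minutes after the first.
- The size depends wholly on an assumed episode length and vanishes at 30 minutes or more.
- It is also tempting to say that minutes below 75 are known only to the width of the plasma gap. The SAP names plasma for below 60, not for below 75, and in the protocol's alert rule 75 is a sensor value. The defect there is an unnamed source and method.
- It is not settled that the second dose has its first sample only at 15 minutes. The listed grid refers to glucagon administration in general, and a grid running to 120 minutes after the first dose would overlap the period after a second.

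These points limit the size and certainty of the concern. What stands is that, on any reading, gaps of 10 to 15 minutes or more open from 10 minutes after the dose, and no rule says how a plasma-based count handles them.

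**Conclusion.** The concern holds as a limited measurement weakness. Short plasma values below 60 can fall between post-dose samples and be scored as prevented, and for that count the error runs only in the system's favour. Under uniform onset, the share unseen over 0-120 minutes runs from 70% at 5 minutes to 20% at 20 minutes and zero at 30 on the listed times. If the 15-minute checks count from 30 minutes, it runs from 61% at 5 minutes to zero at 15. For time below 75, the finding is only that source and method are unspecified; if minutes were interpolated from plasma, individual errors could go either way.

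The endpoints affected are secondary. The protocol's 3-of-5 success rule concerns detection and timing of the dose by the algorithm and is untouched. The change is worth making because it is cheap, not because the study's main conclusion depends on it.

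**What to change.** For outcome measurement only, with no change to treatment or clinical monitoring rules:

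1. Continue the protocol's own 5-minute YSI sampling below 90 mg/dl after each dose, in addition to the listed times. This reduces missed lows but does not remove them, because a sample below 90 is needed to start it: a participant at 95 at one draw could fall and recover before the next.
2. In addition, or instead if extra draws are not wanted or sampling is already complete, have the SAP report values below 60 and minutes below 75 from plasma together with the downloaded sensor trace over one stated post-dose window. Name the glucose source for below 75, say how minutes are computed between samples, and give the sampling gap beside each result.
3. Reconcile the post-dose grid, the second-dose schedule and the 15-minute pre-discharge checks, so that it is clear which samples exist at which times after each dose.

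**Cost.** Item 1 needs some extra small draws through the existing line, with the analyser already in the room. Over 120 minutes the ceiling is 24 − 8 = 16 extra draws, reached only if glucose stays below 90 throughout; usually it should be a few. Items 2 and 3 are wording, plus analysis of sensor data already collected. The prevention count may come out less favourable.

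### The glucagon increase above baseline has no defined baseline and no blood sample at dosing; the last glucagon value before either dose can be nearly 30 minutes old

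*Protocol*

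**What the plan says.** All the sampling rules are in the protocol's Brief outline of treatments, Visit Day 3.

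- **Fasting:** "Two blood samples will be obtained for measurement of plasma glucose (via YSI analytical device) immediately and for subsequent hormonal assays".
- **After the meal:** YSI glucose is measured every 10 minutes, and every 5 minutes once venous glucose is under 90 mg/dl. Hormones are drawn less often: "hormonal profiles at 10, 20, 30, 60, 90, 120, 150, and 180 minutes".
- **End of the pre-dose series:** "This blood sampling series will conclude once sensor glucose levels fall to <75 mg/dl".
- **Dosing:** the clock restarts at 0 when glucagon is delivered. Glucose is then measured at 5, 10, 20, 30, 45, 60, 90 and 120 minutes, and "glucagon levels will be analyzed concurrently to determine magnitude of increase above baseline".
- **Just before dosing:** the symptom score is taken "At time of alarm trigger and before each administration of glucagon". No blood draw is listed with it.
- **Second dose:** it may follow 30 to 120 minutes after the first. The monitoring tied to it is glucose every 15 minutes for 60 minutes.
- **Purpose of the glucagon assays:** "to assess endogenous responses as well as post-bolus plasma levels".

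The protocol's Biostatistical Considerations name repeated-measures ANOVA for the hormone profiles. The SAP's Statistics paragraph names the Wilcoxon signed-rank test. Neither identifies a pre-dose glucagon value. The SAP's Study endpoints include prevention of plasma glucose below 60 mg/dL as a secondary outcome.

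**The concern.** An increase above baseline can be interpreted only if the baseline is named and lies close to the dose. Here it could be the fasting sample or the last hormone sample of the meal phase, and the two may give different answers. Both precede the bolus by a period in which the participant has absorbed a meal and glucose is falling, so the participant's own glucagon may have changed. Any such change is counted in the rise reported after the bolus. Before a second dose, glucagon remaining from the first dose is a further component, and no draw is scheduled immediately before that dose to measure it.

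A related but smaller gap affects plasma glucose. The alert is triggered by the sensor, while the below-60 outcome is judged on plasma. With no plasma value at dosing, a first reading below 60 at +5 minutes leaves open whether the fall came before or after delivery.

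**Working it through.** The plan gives no figure to reproduce. The check is the age of the last scheduled sample at the moment of dosing:

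age = dose time − latest scheduled sample time at or before it.

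If dose times are uniform over a window made of intervals of length L, the mean age is Σ(L²/2) / ΣL, and the maximum is just under the longest L.

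**Glucagon before dose 1.** From 30 minutes after the meal the hormone grid is 30, 60, 90, 120, 150, 180. Take doses at 60–180 minutes (assumed window, uniform timing), which is four intervals of 30 minutes.
- Mean = 4 × (30²/2) / 120 = 1800/120 = 15 minutes.
- Maximum: just under 30 minutes. A dose at 89 minutes relies on the 60-minute sample, 29 minutes old.
- Share of dose times with an age above 10 minutes = (30 − 10)/30 = 67%.
- After 180 minutes no hormone sample is listed until the bolus. A dose at 200 minutes has a value 20 minutes old, one at 240 minutes a value 60 minutes old, and so on without limit.

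**Glucagon before dose 2.** The window is 30–120 minutes after dose 1, and the samples within it are at 30, 45, 60, 90 and 120. The intervals are 15, 15, 30 and 30 minutes.
- Mean = (112.5 + 112.5 + 450 + 450)/90 = 1125/90 = 12.5 minutes.
- Maximum: just under 30 minutes.
- Share above 15 minutes = (15 + 15)/90 = 33%.

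**Plasma glucose before dose 1.** At the alert the last YSI value is at most 5 minutes old if venous glucose is under 90, or at most 10 minutes if not. Any delay from alert to dose adds to this, and the documents do not state one. The relevant margin is the last YSI value minus 60. Participants who could cross 60 unseen before dosing are those whose last YSI lay between 60 and 60 + rate × gap. The rates, 1 to 3 mg/dl per minute, are assumed.

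| Gap to dosing | Rate 1 | Rate 2 | Rate 3 |
|---|---|---|---|
| 5 min | 60–65 | 60–70 | 60–75 |
| 5 min + assumed 5 min delay | 60–70 | 60–80 | 60–90 |

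In the 10-minute case the last YSI was at least 90. Falling below 60 within 10 minutes needs more than (90 − 60)/10 = 3 mg/dl per minute, which is outside the assumed range unless dosing is also delayed.

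**The case against.** The strongest reply is that the schedule already covers most of this, and that the glucagon rise is a descriptive assay rather than a listed endpoint. Four parts of that reply stand, and each rules out a stronger reading.

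- **Plasma glucose.** A reader might infer that plasma already below 60 at dosing cannot be identified. For dose 1 that goes too far. In-room YSI runs every 5 minutes below 90 until the alert, so a value below 60 at any of those draws is seen, and another reading follows at +5 minutes. Only a crossing between the last pre-alert draw and dosing is ambiguous. It is also tempting to treat 75 minus 60 as the safety margin, but 75 is a sensor trigger and 60 a plasma threshold.
- **Separating the two sources of glucagon.** A reader might infer that the trial set out to split endogenous from infused glucagon and cannot. The protocol says only that the assays assess both. The meal-phase samples do describe the endogenous response, though too sparsely to fix the level at dosing.
- **Second dose.** It might be said that carry-over from dose 1 cannot be allowed for at all. Glucagon from the dose-1 series is sampled at 30, 45, 60, 90 and 120 minutes, so there is some information, and no dose-2 increase is specified.
- **Splitting the below-60 outcome** by plasma glucose at dosing is a preference. A late alert is also a failure to prevent, and five planned or seven enrolled participants would leave only a few cases in each group.

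A site might also draw blood at the alert as the closing sample of the series. The text does not say so, and its lists contain no time-0 entry. None of this supplies a definition of baseline or a glucagon value at dosing.

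**Conclusion.** The point holds for glucagon. The protocol plans to report an increase above a baseline that neither document defines, and it schedules no sample at the moment from which the increase should be counted. Followed as written, the nearest earlier value is on average 15 and up to nearly 30 minutes old before dose 1, and on average 12.5 and up to nearly 30 before dose 2. If the fasting sample is taken as baseline, the gap is longer. The averages rest on uniform dose times and, for dose 1, on a 60–180 minute window; the maxima within those windows follow from the schedule alone. How far endogenous glucagon moves in that time is not given, so the size of the resulting error in the rise is unknown.

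For plasma glucose the point is limited to readings below 60 first seen at +5 minutes. The bands above depend on assumed fall rates and delay.

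Only descriptive and secondary results are affected. The protocol's primary endpoint, detection and timing by the algorithm, does not depend on this sample. The change is worth making because it is cheap.

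**What to change.** State in the Visit Day 3 outline that YSI glucose and glucagon are drawn from the intravenous line already in place immediately before each bolus, alongside the symptom score and without delaying delivery. Define that value, in the protocol and the SAP, as the baseline for the glucagon increase after that dose.

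The SAP describes enrollment in the past tense. If sampling is already complete, name the sample used as baseline, report its age at dosing for each participant, and say that the rise includes any change in glucagon over that interval.

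The cost is one or two extra tubes per participant and a sentence in each document, with no extra visit or staff. The draw removes only endogenous change up to dosing. With no undosed comparison, glucagon that the participant releases after the bolus stays in the measured rise, and the report should say so.
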